**11.0 Statistical/Data Analysis Plan**

**11.1 Statistical Considerations:**

List the statistical methods to be used to address the primary and secondary objectives, specific aims, and/or research hypotheses. Explain how missing data and outliers will be handled in the analysis. The analysis plan should be consistent with the study objectives. Include any subgroup analyses (e.g., gender or age group). Specify statistical methods and variables for each analysis. Describe how confounding variables will be controlled in the data analysis

It is hypothesized that each intervention component will reduce at least some health-risking sexual behaviors (HRSBs) and increase health-promoting behaviors (e.g., condom use, obtaining effective contraception) and that each component will increase at least one antecedent to behavior--knowledge, motivations, or perceptions of behavioral skills. It is expected that each intervention component will have a small-to-medium effect on associated outcomes. Descriptive statistics will be calculated for all data including demographics and outcome variables (e.g., scale scores for attitudes, rates of condom use). Effect coding will be used to indicate the presence or absence of each intervention component. Per the multi-phase optimization strategy (MOST) framework, factorial analysis of variance will be used to calculate both main effects and the theoretically-relevant two-way interaction effects. Secondary analyses will be conducted to examine the information-motivation-behavioral skills (IMB) model whereby behavioral skills serves as a mediator between information and behavior change and between motivation and behavior change. Statistical software such as SAS and R will be utilized for analyses.

Interview data (typed notes) will be analyzed using framework matrix analysis.

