The epidemiological risk scenario component involves tailored epidemiological risk information about relative risk of contracting a sexually transmitted infection (STI) and/or having an unintended pregnancy. Relative risk information will be determined by adjusting variables within the component (e.g., number of partners within the last month, percent of time using condoms). The epidemiological risk component is a randomized component and will be "on" or "off". In this component a participant will be able to set different factors (e.g., number of sexual partners, frequency of use of contraception/other preventative measures) and then "run" a simulation which shows a survival curve, or some other graphic, of his or her likely risk for contracting STI or experiencing unplanned pregnancy.

Participants will be emailed a link to complete the Participant Pre-Intervention Assessment (attached) in an online data collection software (e.g., REDCap, SurveyMonkey). The Pre-Intervention Assessment will be identified by RIN only. All questions must be answered. However, a participant may respond that she or he "Prefer Not to Answer" for any question. It is anticipated that this questionnaire will take a participant approximately 20-30 minutes to complete.

After completing of the Participant Pre-Intervention Assessment, a participant will be given an access code and PIN to use to access the app. She or he will then be instructed to download the application (app; intervention) to her or his smart phone (Andriod or iOS). A USU-based research team member will provide these codes and instructions to participants. Once the app is downloaded, a participant will open the app and immediately be prompted by the app to enter the given access code and PIN. After the access code and PIN are entered, the participant will be asked to complete the in-app SRH Knowledge Pre-Test Assessment (attached).

The SRH Knowledge Pre-Test Assessment will assess baseline SRH knowledge that will determine educational content received in the intervention. For example, if a participant answers the pre-test question(s) related to female reproductive anatomy correctly, then she or he will not have female reproductive anatomy content in the educational component of the intervention. All questions in the SRH Knowledge Pre-Test Assessment must be answered. After completion of the SRH Knowledge Pre-Test Assessment, the participant will complete the intervention in the app

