## **10.2 Data Collection:**

Describe all the data variables, information to be collected, the source of the data, and how the data will be operationally measured.

There are four assessments associated with this study: the Eligibility Screening Assessment, Participant Pre-Intervention Assessment, SRH Knowledge Pre-Test Assessment, and Participant Post-Intervention Assessment. The measures used in these assessments are in the attached "Measures" document. In addition to these assessments, data will also be collected on application (app; the intervention) usage and interaction. All Eligibility Screening Assessment data will be anonymous. All other data will be identified by a research identification number (RIN), not by participant name or any other identifying information. RIN will be assigned in the electronic data collection software (e.g., REDCap, SurveyMonkey) when a participant begins a Pre-Intervention Assessment. A master document linking a participant's identity with her or his RIN will be accessible only by the PI and designees at the Unifromed Services University of the Health Sciences (USU).

The Eligibility Screening Assessment is an anonymous screening assessment that will be administered to prospective participants electronically via an online data collection software (e.g., REDCap, SurveyMonkey). The Eligibility Screening Assessment will ask questions related to eligibility (e.g., age, military status) and, to ensure a purposive sample, demographics (e.g., gender, rank, military branch). All questions in the Eligibility Screening must be answered for an individual to be considered for eligibility in the research study.

The Participant Pre-Intervention Assessment will be administered to participants electronically via an online data collection software (e.g., REDCap, SurveyMonkey) following completion of informed consent. The Participant Pre-Intervention Assessment will collect demographic information and assess sexual and reproductive health (SRH) knowledge, attitudes, self-efficacy, sexual behavior, healthcare experiences, healthcare provider interactions, and general mental health. All questions in the Participant Pre-Intervention Assessment must be answered. However, a participant may mark that she or he "Prefer Not to Answer" for any question.

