The SRH Knowledge Pre-Test Assessment will be administered to participants in the application at the onset of the intervention. The SRH Knowledge Pre-Test will assess baseline SRH knowledge that will be used to tailor select content in the app to the participant (see Study Procedures for more information and examples).

The Participant Post-Test Assessment will be administered to participants after completion of the intervention via an online data collection software (e.g., REDCap, SurveyMonkey). All questions in the Participant Post-Test Assessment must be answered. However, a participant may respond that she or he "Prefer Not to Answer" for any question. The Participant Post-Test Assessment assess sexual and reproductive health (SRH) knowledge, attitudes, self-efficacy, and acceptability of the intervention.

Data will also be collected on participants' interactions with the app. This data includes information such as information on how long participants spent on each component, how many times participants opened the app, and how many times participants accessed and completed components.

Participants who consent to opt-in to an additional structured, qualitative interview will be asked to complete an interview with a member of the USU team via telephone two-to-six weeks after receiving the intervention. The interview will ask participants about their experiences using the app, including-but-not-limited-to questions about graphics (aesthetics), barriers to use, and ease of use (see attached interview agenda). Interviews will be recorded, and recordings will be used to expand notes taken during the interview. Recordings will be deleted upon completion of interview notes.

**10.3 At any point in the study, will you request, use, or access health information in any form, including verbal, hard copy and electronic?**

Yes  No

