#### **11.6 Data Analysis Plan: Complete description: Background, Objectives, Design, Step by Step how the project is going to be done, Data analysis plan:**

Data analysis will be conducted consistent with the methods described in the "Statistical Considerations" section.

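### The factorial model in 11.1 leaves out the baseline knowledge, attitude and self-efficacy scores the trial already collects; adding them buys precision at almost no cost

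*Combined protocol and SAP*

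**What the plan says.** Section 11.1 plans effect coding of the five on/off components and states that "factorial analysis of variance will be used to calculate both main effects and the theoretically-relevant two-way interaction effects". It names no baseline score, sex term or other covariate, and does not say whether the dependent variable is the follow-up score or the change from baseline. The form's instructions at the head of that section include "Describe how confounding variables will be controlled in the data analysis" and "Explain how missing data and outliers will be handled in the analysis"; the answer addresses neither. Section 11.6 adds nothing, since it only refers back: "Data analysis will be conducted consistent with the methods described in the" Statistical Considerations section.

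Section 10.2 says the Pre-Intervention Assessment will collect demographics and "assess sexual and reproductive health (SRH) knowledge, attitudes, self-efficacy, sexual behavior", among other topics. The follow-up assessment will "assess sexual and reproductive health (SRH) knowledge, attitudes, self-efficacy, and acceptability of the intervention". So three constructs are measured at both times; sexual behavior is listed only at baseline.

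Section 10.1 fixes the order: "After completing of the Participant Pre-Intervention Assessment, a participant will be given an access code and PIN". The baseline scores therefore precede exposure to any component.

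Section 11.5 gives 720 analysed participants for 80% power at a 5% level to detect small main and interaction effects, and 900 enrolled to allow for 20% attrition. It puts no number on small and does not state sidedness. Section 11.1 adds: "It is expected that each intervention component will have a small-to-medium effect on associated outcomes".

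**The concern.** In a randomized comparison, a score taken before exposure that correlates with the outcome explains part of the residual variance. Leaving it out makes every main effect and interaction less precise than the collected data allow.

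That matters here because section 9.3 uses the experiment to decide which components give the greatest improvements within 25 minutes of content. The decision rests on comparing component estimates, so narrower intervals help even where a single test is adequately powered. Naming the model in advance also settles whether improvement means the follow-up score, the change score or the adjusted score, a choice otherwise open until the data are in hand.

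The components are randomized, so the purpose is precision, not control of confounding.

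**Working it through.** **Inputs from the documents.** 32 conditions (10.1); 720 analysed, 80% power, 5% level, 20% attrition (11.5); effect coding with main effects and two-way interactions (11.1).

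**Assumptions.** Two-sided test; equal allocation, so 360 at each level of a component; unadjusted means follow-up scores only; a standardized effect d; a correlation r; a share m of completers with a missing baseline score. None of d, r or m is in the documents.

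**Step 1: the plan's own figures.** 720 / (1 - 0.20) = 900, which reproduces. The 720 cannot be reproduced exactly because small has no number. At d = 0.20, two-sided, the normal approximation needs 786; d = 0.21 needs 712. By the noncentral t, 720 gives 80% power at d = 0.209.

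**Step 2: power with and without the baseline score.**

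Noncentrality = d × sqrt(N/4) / sqrt(1 - r²(1 - m)).

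Residual df are 720 - 16 = 704 without the covariate (intercept, 5 main effects, 10 two-way interactions) and 703 with it. At d = 0.20, d × sqrt(720/4) = 0.20 × 13.416 = 2.683. With r = 0.3 and m = 0 this becomes 2.683 / sqrt(0.91) = 2.813; with r = 0.5, 2.683 / sqrt(0.75) = 3.098.

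| Power at d = 0.20 | r = 0.2 | r = 0.3 | r = 0.5 |
|---|---|---|---|
| No baseline score | 76.4% | 76.4% | 76.4% |
| Baseline complete | 78.1% | 80.2% | 87.2% |
| 10% mean-filled | 77.9% | 79.8% | 86.1% |
| 20% mean-filled | 77.7% | 79.4% | 85.0% |

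With r = 0 and the covariate still in the model, power is 76.4%, so a useless covariate costs nothing visible. At r = 0.3, power drops below 80% once the mean-filled share passes about 5%. At d = 0.25, power is 91.8% unadjusted, 94.0% at r = 0.3 and 97.2% at r = 0.5.

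**Step 3: equivalent sample size**, 720 / (1 - r²(1 - m)).

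- Complete baselines: 720/0.96 = 750, 720/0.91 = 791, 720/0.75 = 960. That is 30, 71 and 240 extra completers at r = 0.2, 0.3 and 0.5.
- 10% mean-filled: 720/0.964 = 747, 720/0.919 = 783, 720/0.775 = 929. That is 27, 63 and 209 extra.

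**Step 4: precision.** The 95% half-width of a component effect is 1.963 × sqrt(4/720) × sqrt(1 - r²): 0.146 SD unadjusted, 0.140 at r = 0.3 and 0.127 at r = 0.5.

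**Step 5: interactions.** The same figures apply to an effect-coded interaction of equal size. An effect-coded interaction of d is a difference of 2d between simple effects. A 0.20 SD difference between simple effects is therefore d = 0.10, with power 26.8% unadjusted, 29.0% at r = 0.3 and 34.0% at r = 0.5.

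**Step 6: simulation.** With 10,000 simulated trials per setting, 32 cells of 22 or 23, and one main effect and one effect-coded interaction of 0.20 SD, power (main / interaction) was 80.3% / 79.8% at r = 0.3 and 86.5% / 87.4% at r = 0.5. With 10% of baselines mean-filled it was 79.9% / 79.7% and 85.6% / 86.7%. With no true effects, r = 0.5 and 10% mean-filled, rejection was 5.0% / 4.7%, so the filling rule did not inflate type I error.

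**The case against.** **The plan may intend change scores.** The dependent variable is never stated, and 9.3 speaks of improvements, so the baseline may not be wholly unused. That is fair, and the unadjusted figures above do assume follow-up scores only. The recommendation survives. With equal variances a change score has variance 2(1 - r) against 1 - r² after adjustment: 1.40 against 0.91 at r = 0.3, and 1.00 against 0.75 at r = 0.5. Adjustment is never less precise, and for r up to 0.5 the gain over change scores is at least as large as the gain shown.

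**The gain may be small.** 11.1 expects small-to-medium effects, and power is already 91.8% at d = 0.25. At r = 0.3 the half-width moves only from 0.146 to 0.140 SD. The larger gains need r near 0.5, which nothing in the documents supports. For knowledge, r may be low, because the basic education is tailored to the in-app knowledge pre-test and may level participants. This stands: the omission is certain, the size of the benefit is not.

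**The scales cannot be seen.** The measures are in an attachment not available here, so only matching constructs can be confirmed. That limits the figures but not the principle, which needs correlation and not identical scales.

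**Randomization may come before the baseline assessment.** 10.1 and 10.2 leave this open. The score still precedes app access, and is a valid covariate provided participants do not yet know their condition.

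**Other gaps remain.** The change does not cover outcomes lost to attrition or sexual behavior. Those are limits of scope and do not count against it.

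**Conclusion.** The point holds. The plan specifies an unadjusted factorial model although three of its outcomes have a baseline measure taken before exposure, and using that measure is a better model on data already collected. The benefit runs from nothing at r = 0 to the equivalent of 240 more completers at r = 0.5 with complete baselines; at r = 0.3 it is 71. At an assumed d of 0.20, an r of about 0.3 with nearly complete baselines lifts power from 76.4% to just over 80%.

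It should be made because the cost is trivial, not because the trial is underpowered. All sizes rest on the assumed d, r and m, a two-sided test and a comparison with follow-up scores alone. The finding is confined to knowledge, attitudes and self-efficacy.

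**What to change.** Add to 11.1:

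> The effect-coded factorial model for knowledge, attitudes and self-efficacy will each include, as a covariate, that outcome's score from the Pre-Intervention Assessment. Where that score is missing or cannot be formed because of Prefer Not to Answer responses, it will be replaced by the overall mean of the score, computed without regard to condition, so that no completer is dropped.

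State in the same place that the dependent variable is the follow-up score, and when unanswered items make a scale score missing. Sex, the stratification factor in 10.1, is also absent from the model and can be added in the same sentence.

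Keep 720 completers and 900 enrolled; the unknown correlation is no basis for reducing either. As a secondary reporting point, 11.5 should give the planning effect size, the sidedness, and the scale on which the interaction effect is defined.

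The cost is two sentences in 11.1, a clarification in 11.5, and one residual degree of freedom per model for the baseline score (one more if sex is added). No participant, visit or question is added.

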#### **9.5 Target Population:**

Describe the population to whom the study findings will be generalized

Active duty service members, across all services.

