Participants will be randomized to one of the 32 treatment conditions, corresponding to all factorial combinations of randomized components. The randomization scheme will be generated based on a permuted block randomization procedure, with small random sized blocks. Randomization will be stratified by sex. The length of the intervention will vary based on which components (which treatment condition) the participant receives. The components include: (1) a basic sexual and reproductive health (SRH) education (not randomized), (2) video narratives, (3) skills building videos, (4) interactive scenarios, (5) a future life planning tool, and (6) epidemiological risk scenario.

The basic SRH education component is the only component that every participant will receive; all other components will have two levels (i.e., "on" or "off"). The exact educational content the participant receives in this component will be determined based on baseline SRH knowledge, which will be assessed in a pre-test (discussed below). In the basic SRH education component in

the app, participants will be presented with a series of screens with interactive content and occasional videos.

The narrative video component contains videos about situations related to SRH. This component is randomized and is either "on" or "off" (i.e., received or not received by a participant). Narrative videos will include stories of individuals engaging in positive and negative sexual health behaviors that leads to either positive and negative outcomes, respectively. Those who receive the narrative video component in the app will be expected to watch the assigned videos.

The skills building video component contains videos on how to perform or engage positive SRH behaviors, such as correctly using a condom and what to expect when having a Pap smear. This component is randomized and is either "on" or "off". Participants who receive this video component in the app will be expected to watch the assigned videos.

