**11.5 Please provide a justification for your sample size**

Power analysis indicates that a sample of 720 will be sufficient to have 80% power to detect small main effects and interaction effects at a 5% significance level. Accounting for 20% attrition, up to 900 service members will be enrolled to reach target sample size.

Of this total sample, it is anticipated that 40 participants will be needed and selected to complete an interview. Qualitative data analysis does not lend itself to power analysis. Sample size was selected based on the experiences of our qualitative experts.

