## 13.0 Recruitment and Consent

### 13.1 Please describe the recruitment process, including how subjects will be identified and selected for the study.

Participants will be recruited across services via advertisement (e.g., physical posters, social media, condoms, nominal items like stress balls), word of mouth, or by approaching or being approached by a research team member, as well as via email or listserv. Individuals who express interest in taking part in the study will be asked to provide consent to be screened for eligibility (Eligibility Screening Questionnaire attached). After completing the screening, eligible individuals will be asked to provide informed consent, which will be collected by USU-based research team members.

The study sample will represent a convenience sample of individuals who voluntarily express interest in participating. Purposive sampling will also be employed to ensure adequate representation of female and male participants and each branch of the military. Participants will complete the intervention off-duty to minimize impact on military operational effectiveness.

Purposive sampling will also be employed when selecting interview participants from the group of participants who consented to complete an interview if selected. Participants will be selected to ensure appropriate representation of gender, sexual, and/or ethnic/racial identity and military rank and/or service and to ensure that there is a good mix of those who have and have not used the app. Demographics information from the Pre-Intervention (baseline) Assessment and analytics data on app use will be used to inform the selections. It will still be expected that participants complete this part of the study off duty as well.

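### Randomisation is stratified by sex, but 11.1 models component terms only: sex is left out and no sex-specific component effect is prespecified

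*Combined protocol and SAP*

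**What the plan says.** All references are to the combined protocol and SAP.

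- **Randomisation (10.1).** Each participant is allocated to one of 32 conditions, the full crossing of five on/off components. "Randomization will be stratified by sex". Sex is the only stratification factor named.
- **Content (10.1).** The skills building videos, a randomised component, give as examples "correctly using a condom and what to expect when having a Pap smear".
- **Recruitment (13.1).** The sample is a convenience sample, with this addition: "Purposive sampling will also be employed to ensure adequate representation of female and male participants and each branch of the military". No target split between women and men is given.
- **Population (9.5).** Findings are to apply to "Active duty service members, across all services".
- **Analysis (11.1).** Effect coding marks each component as present or absent, and "factorial analysis of variance will be used to calculate both main effects and the theoretically-relevant two-way interaction effects". The interactions are not listed. The form's prompt asks for subgroup analyses and offers gender as an example; the answer names none. Section 11.6 only points back to 11.1.
- **Use of the results (9.3).** The component effects guide the choice of one package of at most 25 minutes, and the team then judges whether it is ready for a randomised trial.

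**The concern.** A pooled main effect averages the effect in women and the effect in men, weighted by how many of each were analysed. If the two effects are equal, the weights do not matter. If they differ, the result describes the recruited mix, and that mix is partly a recruitment choice. With Pap smear material in one randomised component, equal effects in both sexes cannot be presumed for it.

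Two things are at stake. The estimate may not carry over to the population in 9.5. And a component that helps mainly one sex may look weak, or adequate, in the average, with no planned table to show it. Separately, leaving the stratification factor out of the model departs from the usual practice of analysing in line with the randomisation.

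**Working it through.** **Inputs from the documents.** Analysed sample 720 and 5% significance level (11.5); about half the sample on and half off for each component (10.1).

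**Assumptions.** Two-sided test (sidedness is not stated); SD = 1; the sex-specific effects; a recruited share of women p of 20% to 60%; an active duty share of women w of 15% to 25%. The documents give none of these.

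**The plan's own figure.** "Accounting for 20% attrition, up to 900 service members will be enrolled to reach target sample size": 720 / (1 − 0.20) = 900, which reproduces. The 720 itself cannot be reproduced, because 11.5 puts no number on a small effect. At 720, 80% two-sided power corresponds to 0.209 SD, so the figure is plausible. The present point does not depend on it.

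**Step 1: pooled effect and power.**
Pooled effect = p × (effect in women) + (1 − p) × (effect in men).
SE of a component effect = 2/√720 = 0.0745 SD.
Power is from the non-central t distribution with 718 degrees of freedom.

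| Women / men (SD) | Women recruited | Pooled effect (SD) | Effect / SE | Power |
|---|---|---|---|---|
| 0.40 / 0 | 50% | 0.20 | 2.68 | 76% |
| 0.40 / 0 | 20% | 0.08 | 1.07 | 19% |
| 0.30 / 0.10 | 50% | 0.20 | 2.68 | 76% |
| 0.30 / 0.10 | 20% | 0.14 | 1.88 | 47% |
| 0.25 / 0.15 | 50% | 0.20 | 2.68 | 76% |
| 0.25 / 0.15 | 20% | 0.17 | 2.28 | 62% |
| 0 / 0.30 | 20% | 0.24 | 3.22 | 90% |
| 0 / 0.30 | 60% | 0.12 | 1.61 | 36% |

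The first pair of rows is an extreme case and the 0.25 / 0.15 pair a mild one. The last two rows show that the problem runs in both directions.

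**Step 2: the target population.** Replace p by w. For 0.40 / 0, the effect standardised to 15–25% women is 0.15 × 0.40 = 0.06 to 0.25 × 0.40 = 0.10 SD, against 0.20 SD in a 50:50 sample. For 0.25 / 0.15 it is 0.15 + 0.15 × 0.10 = 0.165 to 0.15 + 0.25 × 0.10 = 0.175 SD, against 0.20 SD.

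**Step 3: how well a sex difference can be estimated.**
SE of the difference = √(4/N_women + 4/N_men).
- 360 and 360: √(0.0111 + 0.0111) = 0.149 SD
- 144 and 576: √(0.0278 + 0.0069) = 0.186 SD

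Multiplying by 1.96 + 0.84 = 2.80 gives differences of about 0.42 and 0.52 SD detectable with 80% power.

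**Step 4: chance findings.** Suppose no true sex difference exists. An estimated difference beyond ±0.20 SD then has probability 0.180 (SE 0.149) or 0.283 (SE 0.186) per component. For at least one of five, treating the estimates as independent: 1 − 0.820⁵ = 0.63, or 1 − 0.717⁵ = 0.81, for each outcome.

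**Step 5: degrees of freedom.** With five main effects and all ten two-way interactions among components, 720 − 1 − 5 − 10 = 704 remain. Sex and five component-by-sex terms take six, leaving 698.

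**The case against.** The strongest reply is that stratification balances every component within each sex, so the pooled effect is a sound causal estimate. That stands: there is no confounding, and the question is only which population the average describes and what it may hide.

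Several stronger readings are tempting, and the documents do not support them.

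- *Several components are sex-specific.* Only the Pap smear item is explicitly so within a randomised component. The risk scenario tool in 10.1 is written for users of either sex. Female anatomy content sits in the non-randomised education component and depends on pre-test answers. The documents do not say whether men are assigned the Pap smear video.
- *Women will be over-recruited.* Section 13.1 promises adequate representation and states neither a split nor oversampling.
- *A component would be kept or dropped on significance.* Section 9.3 refers to the greatest improvements within the time limit and to team judgement. The power figures above are chances of a significant result, not selection outcomes.
- *The team could not see a sex difference.* Sex is recorded for stratification, so results can be split later. What is missing is prespecification.
- *A sex interaction is ruled out.* The interactions in 11.1 are unlisted, so one is not expressly excluded; but the coding described covers components only, and nothing commits the team to it.

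It is also fair to say that 0.40 against 0 SD is extreme, since 11.1 expects a small-to-medium effect from each component, and that the milder case moves power only from 76% to about 62%. Finally, sex-specific estimates will be noisy. Acting on them without restraint could replace dependence on the sex mix with selection by chance (Step 4). That objection shapes the fix.

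**Conclusion.** The concern holds as a gap in the planned model and its reporting. The stratification factor is absent from the analysis, and no sex-specific or standardised component effect is prespecified, although the form's prompt invites it and the design supports it. The pooled effects remain valid for the recruited mix, so the planned analysis is incomplete, not wrong.

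How much it matters rests entirely on assumed effects and sex mixes. Moving from 50% to 20% women takes power from 76% to 19% if a component works only in women (0.40 SD), and from 76% to about 62% if the effects are 0.25 and 0.15 SD. If effects are equal in both sexes, the pooled effect does not depend on the mix. A reader might infer that the wrong components will be chosen; the documents support only that the planned analysis would not show whether the sex mix had influenced the result. This is a cheap improvement worth making before analysis.

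**What to change.** In 11.1:

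1. Add effect-coded sex to the factorial model. Keep the pooled component main effect from that model, without component-by-sex terms, as the basis for component selection.
2. Prespecify, as secondary, the same model with the five component-by-sex terms. With ±1 coding, the component coefficient in this extended model is the equally weighted average of women and men, so it should not be substituted for the pooled effect in item 1.
3. For each component, report the effect in women, the effect in men, and the effect standardised to the active duty sex mix, w × (effect in women) + (1 − w) × (effect in men), each with a 95% interval. State the source of w.
4. State that these results are descriptive. They flag components for further checking and are not keep/drop tests.

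Stating the intended split between women and men in 13.1 would also help readers interpret the pooled effect.

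**Cost.** About six degrees of freedom out of roughly 700, one extra table, and no new participants or data. The drawback is imprecision: sex differences carry an SE of 0.149 to 0.186 SD, so only differences of about 0.42 to 0.52 SD are detectable with 80% power. Standardising also costs some precision. In a 50:50 sample with w = 0.15, the SE is √(0.15² × 4/360 + 0.85² × 4/360) = 0.091 SD, against 0.0745 SD for the pooled effect.
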